Variation in Urine Electrolytes, pH and Specific Gravity Throughout the Day and the Effect of Increased Fluid Intake on Intra-Day Urine Composition

NCT03645785

PRINCIPAL INVESTIGATOR:

[name] Urology

Albany Medical College [name] [contact]

Co-Investigator:

[name] Urology

[name]

Albany Medical Center
[name]

A. STUDY BACKGROUND AND PURPOSE

Nephrolithiasis has an estimated global prevalence of 10-15%, with North America encompassing a larger prevalence compared to Europe and Asia, with the exclusion of Saudi Arabia.^[1, 2] Kidney stones have a higher incidence in working adults compared to children and the elderly, and 50% of those who have had kidney stones are likely to develop another episode in the next 5 years, which places a heavy economic burden as those with kidney stones are likely to miss work for pain or medical intervention.^[2, 3]

As part of the metabolic work-up for those who have an episode of a kidney stone, the American Urological Association guidelines advocate for a 24-hour urine sample on a random diet, which should be evaluated for volume, pH, calcium, oxalate, uric acid, citrate, sodium, potassium and creatinine. Further, the AUA recommends collecting a 24 hour urine sample within 6 months of any dietary or medical interventions that are taken for nephrolithiasis, as well as a 24 hour urine sample, at a minimum, annually, after therapy is started to assess for adherence and success. However, 24 hour urine collections are problematic because they are cumbersome to execute, especially in working patients, they are time consuming, compliance is poor, and they are wasteful as up to 1/3 are rejected because of collection errors. [5-7]

An alternative to the 24-hour urine is to utilize the first morning void. Many studies looking at first voids and random spot urines compared to 24-hour collection with respect to electrolyte composition and pH have demonstrated that while there is a correlation, there is a large amount of variability, leading to 24 hour urine collections as maintaining their role as the gold standard. [5, 6, 8] Despite this, random spot voids and first morning voids are still used in practice because they are far more convenient and have the potential to be less expensive, however it is not known whether they are easily reproducible over a period of office visits and medically informative.

Spot-urines are assessed for pH and specific gravity, as well as their electrolyte compositions by indexing the electrolyte compositions compared to the creatinine excretion as the creatinine excretion is stable over 24-hours and is independent of the void volume.^[5, 7, 9, 10] First morning void samples compared to random day voids are thought to be the best estimates to assess because they are more likely to represent the most concentrated specimens due to the relative dehydration overnight while an individual is asleep.^[10]

However, first voids are difficult to attain in patients as clinic appointments vary in time throughout the day, and freshly voided samples of urine should be analyzed within 4 hours of void if they are refrigerated, and within 2 hours of void if left at room temperature. [10, 11] pH for example, can change for more alkaline urine if it is handled aggressively or as a result of the evaporation of carbon dioxide, and urine with urease containing bacteria can have its pH changed as a result of urea break down into ammonia and carbon dioxide [12, 13] Thus, in the clinical setting, voided samples are usually taken at the time of the appointment to assess for pH and electrolyte composition.

Unfortunately, little is known about the variation in excretion of electrolytes such as calcium throughout the course of the day. While many studies have looked at the composition of urine from a single sample compared to 24 hour sample, the hour to hour variations of excretion has not fully been elucidated. This is especially important because factors like temporal changes and orthostatics have already been shown to play a role in altering urinary protein excretion. Turney chemical composition is altered by pre vs post prandial state, water intake, and specific diet changes. A state of this study will be to evaluate the intra-day changes (from the morning through the

workday) of urinary composition within a person. This will help to validate the use of spot-urines during clinic appointments in the outpatient urology setting.

Further, AUA guidelines for stone formers is to have a target urine volume output of 2.5L as the primary treatment option in those who are not fluid restricted secondary to renal or heart disease. [4] Multiple studies have demonstrated that increasing fluid intake leads to a reduction in kidney stones, as well as the general observation that non-stone formers have a larger mean urine volume compared to stone-formers. [2, 15] In the clinical setting, the clinician can assess hydration beyond measuring urine volumes is looking at specific gravity as a metric of assessing relative hydration. [12] However the hour to hour changes related to someone who increases their fluid intake have not been evaluated. Thus, we posit to assess how doubling oral fluid intake impacts chemical composition, pH and specific gravity over the course of a day. Similarly, increasing citrate consumption is also recommended but little is known about the hour to hour changes in the urine as a result.

Hypothesis:

- 1) 1st morning spot urine is more concentrated than others during the day, and the excretion of calcium and other electrolytes will significantly vary during the day.
- 2) Increasing fluid intake reduces urinary concentration but does not change calcium excretion.

B. STUDY DESIGN

Research team will consent subjects in the Urology Clinic office. Subjects will all get a questionnaire asking about weight, height, history of kidney stones, whether they are on any diuretics, medications that alter urine chemistries, or special diets.^[14] BMI will be calculated and stratified to assess whether the day-to-day variations are different for those with larger BMI. **Those taking diuretics, have known kidney disease or history of known nephrolithiasis will be excluded.** Those that do not comply with the void times on Day 1 and 2 will be excluded. ^[10]

Subjects will receive 4 sterile cups and receive education on mid-stream urine collection. Day 1 will begin 5p.m. on the day before first morning void is collected. Subjects will collect 20-30 ml urine per collection. The cup will be marked at the 20-30 ml line to indicate how much urine should be collected. First morning voids: Subjects will be instructed to refrigerate their first voids. [10, 17] Time of void and time of presentation of specimen to study representative will be recorded to track how the length of that interval affects composition. The 2nd, 3rd and 4th void samples will be collected in the office during the designated times, and given to study personnel for dipstick analysis. Subsequently, the samples will be frozen, and batch sent to Litholink (Litholink, LabCorp Specialty Testing Group, Corporate Office [name]).

Table 1 – Study schematic

	Day 1	Day 2	Day 3	Day 4
	5 pm day before – 5pm	5 pm – 5pm	5 pm – 5pm	5 pm – 5pm
Fluid intake Record volumes and times of day True Lemon drink mix in one	Normal intake – record all	Normal intake – record all 5 pm – 12 am: Drink one bottle	Double daily intake - record all 5 pm – 12 am: Drink one bottle	Double daily intake - record all 5 pm – 12 am: Drink one bottle
bottle of Poland Spring water, 16.9 oz (500 mL)		Brillik One bottle	Dillik one bottle	Dillik one bottle
Urine void times - record times of all voids, and collect 20 – 30 mL samples at the specified times	First void, 9-10 am, 1-2 pm, 4-5 pm	-	-	First void, 9-10 am, 1-2 pm, 4-5 pm
Food intake – record times of all meals and snacks	Record all	-	-	Record all

1) Day 1: Normal Drinking Habits

- a. Day 1 begins at 5pm (the night prior to the 1st urine collection)
- b. All subjects will collect spot urine sample on the first void at home, then at 9-10AM, 1-2 PM and 4-5PM. They will be provided 4 sterile urine cups labeled for the different timed collections.
- c. Subjects will be educated on how to collect a mid-stream specimen. Females will further be instructed to void normally without cleansing as this adds an extra layer of burden on participants and studies have demonstrated that mid-stream non-cleansed sample is not inferior to a cleansed mid-stream specimen. [11, 16-19]
- d. Starting on Day 1 at 5pm until 5pm the following day subjects will be asked to record the times they eat, and to record their approximate fluid intake. Post-prandial urine excretion may be different compared to other voids. [20]
- e. Subjects will be asked not to void outside of the timed collections. If they do void outside of these times, they will be asked to record the extra times that they void.

2) Day 2 and 3: True lemon Intake

a. Day 2 will begin 5p.m after the last collected void of Day 1.

b. Subjects will be provided 3 True Lemon packets (True Citrus, [name]). They will be instructed to mix 1 packet in one 16.9oz (500 mL) bottle of Poland Spring water (Nestle Waters North America). They will drink one bottle on Day 2 after 5 p.m., and another bottle after 5pm on Day 3, All True Lemon packets and Poland Spring bottles will be provided to subjects by the research study team.

- c. Subjects will be asked to record the time and the approximate volume of their fluid intake. Subjects will record the 2 True Lemon water bottle intakes, as well as any additional fluid intake they have.
- d. On Day 3 all subjects will be asked to double their fluid intake based on the previous days' diaries.

3) Day 4

- a. Day 4 will begin at 5pm (the night prior to urine collection) and the subjects will drink the last bottle of water with True lemon.
- b. All subjects will collect spot urine sample on the first void at home, then at 9-10AM, 1-2 PM and 4-5PM.
- c. Subjects will be asked to record the times they eat, and to record their approximate fluid intake and times of intake. Subjects will also be asked to double their fluid intake, using Day 1 and Day 2 as a guide of their normal daily intake (including the True Lemon Bottle volume).
- d. Subjects will be asked not to void outside of the timed collections. If they do void outside of these times, they will be asked to record the times of the extra voids.
- e. Subjects will be educated on how to collect a mid-stream specimen. Females will further be instructed to void normally without cleansing as this adds an extra layer of burden on participants and studies have demonstrated that mid-stream non-cleansed sample is not inferior to a cleansed mid-stream specimen.^[11, 16-19]
- 4) UA dipsticks will be used in office to evaluate for pH and specific gravity dipsticks are within 0.5 pH effective accurate compared to pH meters.^[21] Dipstick analysis should be done as soon as possible after the urine is collected as pH changes the longer it is left out as a result of the natural breakdown of urea.^[12] It will be analyzed by study coordinators. Samples will also be sent to lab for evaluation of chemical composition of creatinine, citrate, and calcium. Electrolytes will be indexed against creatinine to evaluate their concentrations without having a 24-hour void volume amount.^[5, 9] A pH-meter will also be used to correlate the accuracy of pH values reported by the dipsticks.
- 5) All urines will be frozen immediately upon acquisition until batch sent to Litholink for electrolyte and pH analysis. [10, 17] All samples will only be identifiable by the study identification number. The lab will be instructed to discard all samples after the necessary tests are conducted.
- 6) A sample of citrate-Poland Spring will be sent to Litholink for analysis of Calcium and Citrate for reference.

C. SUBJECT POPULATION

- Healthy adult subjects will be accrued from outpatient urology office employees, residents, medical students, and faculty members who volunteer to participate in the study. A recruitment flyer will be posted in the outpatient Urology office and given to interested persons. A recruitment email will also be sent to office personnel, residents, medical students and faculty.

- The study will recruit 20-30 subjects.

D. DATA ANALYSIS

- Data collected with respect to subject demographics will include that from the questionnaire, including use of medications that affect kidney excretion, body weight and height, age, history of kidney disease or stones, types of diet, and supplements use. These points will be linked with the subject's urinalysis and urine chemistry results, however the subject's name will be removed during the statistical analysis. Data will be stratified by these demographics to identify any patterns that could potentially be studied by future studies.
- Those subjects who identify as having renal disease/history of nephrolithiasis, or who take diuretics will be excluded from the study. Those who are required to be on a fluid restriction for their health will not be allowed to participate in the study for safety reasons. Those that do not have voids at the appropriate time intervals will also be excluded.
- Data analysis will be conducted by [name] and [name] at Albany Medical Center.
- All questionnaires and diaries will be kept in research office, input into password-protected software, and analyzed at Albany Medical Center.
- Data Points: After discussing data points with [name] the study will aim to recruit at least twenty subjects, which will give 87% power to detect a difference in any urine variable that is at least as large as one standard deviation of that variable in the normal fluid intake session (two tailed alpha of 0.05). Since, assuming a normal distribution, one standard will encompass 68% of patients, we consider a one standard deviation difference to be the minimally important clinically significant difference in these measures. Data points will be statistically analyzed by a repeated measures ANOVA test. Further, changes in the below variables after doubling fluid intake will be calculated for statistically significant changes compared to normal fluid intake.
 - o pH
 - o Specific gravity,
 - o Calcium
 - o Creatinine
 - Citrate
 - o Changes in the above after doubling fluid intake

E. RISKS

- There are minimal risks to this study.
- If subjects are on a fluid restricted diet, the second component of the study could potentially be harmful to their health. For this reason, these subjects will be excluded from the study
- There is a risk that there is a violation of privacy due to a breach in study data. However, the data will not be able to be linked to a specific individual.
- There is a risk of exposing underlying illness while evaluating urines of otherwise healthy subjects.

F. BENEFITS

- The main benefits of this study are to improve the quality of care provided to stone-forming patients in the urologic clinical setting.

- Add to the general medical knowledge about urine composition and its variation.

G. CONFIDENTIALITY

- After consent is collected, all subjects will receive and be referred to by a study number ie. 1, 2, etc., which all collected specimens and documentations will utilize. The master key containing the names and corresponding study numbers will be securely stored on an AMC network drive to which only the research staff have access. The master key will be destroyed after all data collection and analysis.
- A portion of the subjects' past medical history and current medication regimens will be collected, but their name will be replaced by a study ID# to de-identify the data please see questionnaire.

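### Hypothesis 2 predicts no change in calcium excretion, but the plan only tests for significant change, which can contradict that prediction but cannot establish it.

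*Combined protocol and SAP*

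**What the plan says.** Section A, Hypothesis 2, makes two predictions: "Increasing fluid intake reduces urinary concentration but does not change calcium excretion". The first is a change. The second is the absence of one.

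Section D (Data Points) gives the whole inferential plan. It states "Data points will be statistically analyzed by a repeated measures ANOVA test" and adds that "changes in the below variables after doubling fluid intake will be calculated for statistically significant changes compared to normal fluid intake". Calcium is listed with pH, specific gravity, creatinine and citrate, and has no separate treatment.

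The same paragraph claims 87% power with twenty subjects, at two-sided alpha 0.05, for a difference "at least as large as one standard deviation of that variable in the normal fluid intake session". It justifies that size by saying "we consider a one standard deviation difference to be the minimally important clinically significant difference in these measures".

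Section B, item 4, defines the measure: "Electrolytes will be indexed against creatinine to evaluate their concentrations without having a 24-hour void volume amount". Table 1 schedules four samples on each of Days 1 and 4 ("First void, 9-10 am, 1-2 pm, 4-5 pm"). Section C says "The study will recruit 20-30 subjects".

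**The concern.** A difference test takes no change as its null hypothesis. Rejecting the null contradicts the calcium prediction. Failing to reject it leaves a range of changes compatible with the data, and only an interval shows how wide that range is.

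The document never says that p > 0.05 will be read as no change. It offers no other way to reach that conclusion, however: no interval, no margin and no decision rule. The 1 SD threshold could serve as a margin, but it is used only to set the sample size.

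Half of one of the two stated hypotheses therefore has no analysis that could support it. The half about urinary concentration is unaffected, because a significance test suits it.

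**Working it through.** **Inputs.** From Section D: n = 20, two-sided alpha 0.05, difference 1 SD, power 87%. From Section C: up to 30 subjects. The correlation rho between a subject's Day 1 and Day 4 values is not given, so 0, 0.3, 0.5 and 0.7 are assumed. SDs are taken as equal on the two days. One paired value per subject stands in for the day contrast of the ANOVA.

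**Step 1: the plan's own figure.** A two-sample t-test with 20 per group and a 1 SD difference has power 86.9%, which matches 87%. A paired t-test with 20 subjects and rho = 0 gives 85.1%. The figure reproduces, but it is power to detect a change.

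**Step 2: precision of the estimated change.** In units of the Day 1 SD, the SD of the change is sqrt(2(1 − rho)), which is 1.414, 1.183, 1.000 and 0.775. The 95% half-width is t(0.975, n − 1) × SD of change / sqrt(n). For n = 20 and rho = 0 this is 2.093 × 1.414 / 4.472 = 0.662.

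**Step 3: how often a real change is non-significant** (paired t).

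| | rho 0 | 0.3 | 0.5 | 0.7 |
|---|---|---|---|---|
| 95% half-width (SD), n = 20 | 0.66 | 0.55 | 0.47 | 0.36 |
| 95% half-width (SD), n = 30 | 0.53 | 0.44 | 0.37 | 0.29 |
| True 0.5 SD change, non-significant, n = 20 | 68% | 57% | 44% | 22% |
| True 0.5 SD change, non-significant, n = 30 | 53% | 39% | 25% | 7% |
| True 1 SD change, non-significant, n = 20 | 15% | 5% | 1% | <0.1% |
| True 1 SD change, non-significant, n = 30 | 4% | 0.6% | <0.1% | <0.1% |

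**Step 4: would an interval rule work at this sample size?** The criterion is that the 90% interval for the change lies inside ±1 SD (two one-sided 5% tests), with the SD estimated from Day 1. The results are from simulation.

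| Criterion met when | rho 0 | 0.3 | 0.5 | 0.7 |
|---|---|---|---|---|
| No true change, n = 20 | 80% | 92% | 97% | 99.7% |
| No true change, n = 30 | 95% | 99% | 99.8% | ~100% |
| True change of 1 SD, n = 20 | 5.4% | 6.5% | 7.4% | 9.7% |
| True change of 1 SD, n = 30 | 5.8% | 6.7% | 7.7% | 10.1% |

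The error rate at a true 1 SD change exceeds the nominal 5% because the margin itself is estimated.

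**Step 5: a tighter margin.** For ±0.5 SD (an assumed value, SD treated as known) and no true change, the chance of success at n = 20 is 4.6%, 17.5%, 39.3% and 74.4%. Reaching 80% would take 70, 50, 36 and 22 subjects.

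**The case against.** The strongest reply is that the test already says something about the plan's own threshold. If a 1 SD change is rarely missed, a non-significant result is some evidence against one. When there is no true change and n = 20, 84%, 95%, 98% and 99.9% of non-significant results already have a 90% interval inside ±1 SD (rho 0, 0.3, 0.5, 0.7). At a true 0.5 SD change the shares are 62%, 80%, 91% and 98%. So at this margin the rule often agrees with p > 0.05. This stands, and it limits the practical harm. It does not give the plan a stated basis for the claim, and at low correlation with about 20 subjects the two do diverge.

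A second reply is that a ±1 SD margin still leaves smaller changes unexcluded. This also stands, and it is why the hypothesis has to be reworded. The intervals would at least show which smaller changes remain possible.

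Third, averaging four voids could hide opposite shifts at different times of day. That is a fair caution. The average corresponds to the day effect in the planned ANOVA, which is kept and can still examine time of day.

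Finally, this is a small volunteer study, and the hypothesis may be only an expectation. Even so, the plan states hypotheses, alpha, power and an important difference, so an interval set against that difference is proportionate.

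**Conclusion.** The concern holds. The planned analysis can refute the calcium half of Hypothesis 2 but cannot establish it, and nothing elsewhere in the document fills the gap. This does not depend on any assumed figure.

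Its size does depend on the unstated correlation. Over 0 to 0.7 with 20 subjects, a non-significant result goes with a 95% interval reaching 0.36 to 0.66 SD either side of the estimate, and a true half-SD change goes undetected in 22% to 68% of studies. Changes of 1 SD are seldom missed. The problem is therefore smaller changes, and the lack of any rule for what may be claimed. The data stay usable. The plan should be amended, and the study does not need redesign.

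**What to change.** Keep the significance test. For creatinine-indexed calcium, add the mean Day 4 minus Day 1 change with 95% and 90% confidence intervals. Base it on each subject's mean of the four timed voids, estimated from the repeated-measures model. Define the SD as the between-subject SD of that same Day 1 mean. State that p > 0.05 alone will not be reported as no change, and fix the wording in advance:

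1. 90% interval within ±1 SD and 95% interval includes zero: *no change as large as 1 SD*.
2. 90% interval within ±1 SD and 95% interval excludes zero: *changed, but by less than 1 SD*.
3. 95% interval excludes zero and 90% interval not within ±1 SD: *changed*.
4. Otherwise: *inconclusive*.

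At a true 0.5 SD change with n = 20, these occur in 42/45/40/21%, 1/9/25/58%, 31/34/32/21% and 25/11/4/0.3% of studies (rho 0/0.3/0.5/0.7). A significant change is always reported as a change. Reword Hypothesis 2 to match, for example that extra fluid alters calcium excretion by less than 1 SD. A tighter margin may be used if justified in advance.

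**Cost.** Analysis wording and two intervals; no new data. The result may be inconclusive. The supported claim is weaker than no change at all. The criterion is wrongly met at a true 1 SD change about 5–10% of the time. A margin near ±0.5 SD could need more subjects than planned. Day 4 also differs from Day 1 by the True Lemon drink, and this change does not separate the drink from the fluid.

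### Section B's void-time exclusion names Day 2, which has no urine collection, and is silent on Day 4; with Section D, one missed window also discards the subject's valid samples from the other day.

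*Combined protocol and SAP*

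**What the plan says.** Two sentences in the protocol govern exclusion for void timing.

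- Section B (Study Design): "Those that do not comply with the void times on Day 1 and 2 will be excluded".
- Section D (Data Analysis): "Those that do not have voids at the appropriate time intervals will also be excluded". No day is named.

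Table 1 gives the collection schedule as "First void, 9-10 am, 1-2 pm, 4-5 pm" under Day 1 and Day 4, with a dash under Days 2 and 3. Items 1b and 3b repeat this for Day 1 and Day 4 in identical words: "All subjects will collect spot urine sample on the first void at home, then at 9-10AM, 1-2 PM and 4-5PM".

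The protocol numbers its days 1 to 4 and uses Day 2 in a specific sense. Item 2a says "Day 2 will begin 5p.m after the last collected void of Day 1", and item 3c has subjects double their fluid "using Day 1 and Day 2 as a guide of their normal daily intake". The items for Days 2 and 3 cover the lemon drink and fluid recording, and schedule no urine sample.

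Hypothesis 1 concerns variation within a day, including that the "1st morning spot urine is more concentrated than others during the day". Section D plans a repeated measures ANOVA and a comparison of doubled with normal fluid intake.

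**The concern.** An exclusion rule fixes the analysis population, so it should point to the days on which compliance can be judged. Section B names one such day (Day 1) and one on which there is nothing to comply with (Day 2). It leaves out the only day sampled under doubled fluid intake. With a target of about 20 subjects, membership of the analysis set should not have to be inferred from a second sentence in another section.

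A further consequence does not depend on the label. Both sentences exclude the subject, not the sample. A subject who gives all four Day 1 samples and then misses one Day 4 window loses the Day 1 samples too. Those samples are valid and bear directly on Hypothesis 1, which needs no Day 4 data.

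**Working it through.** **Step 1: set the rules against the schedule.**

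| Day | Timed voids (Table 1; items 1b, 3b) | Named in Section B rule | Reached by Section D rule |
|---|---|---|---|
| 1 | Four | Yes | Yes |
| 2 | None | Yes | Nothing to apply |
| 3 | None | No | Nothing to apply |
| 4 | Four | No | Yes, by its general wording |

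Section B matches the schedule on Day 1 only. Section D matches it on both collection days. Applied together, the two rules exclude a subject with a missed window on either Day 1 or Day 4.

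**Step 2: check whether the plan's own figure is affected.** Section D states 87% power with 20 subjects for a difference of one standard deviation, two-sided alpha 0.05. A two-sample t calculation with 20 per group has noncentrality 1/√(2/20) = 3.16 on 38 degrees of freedom and gives 86.9%, so the figure is reproduced. A paired t calculation with 20 subjects and an assumed within-subject correlation of 0 gives 85.1%. Neither depends on the exclusion wording.

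Fewer than 20 compliant subjects would lower the figure, but by how much depends on unstated inputs. With 18 subjects the two-sample form gives 83.0%, while the paired form with an assumed correlation of 0.5 gives 97.9%. Section C also allows recruitment of up to 30. No shortfall from the stated power is established.

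**Step 3: illustrate what whole-subject exclusion discards.** The documents give no miss rate, so these are assumed values and not a forecast. Let p be the chance of missing any one clock window, with three windows per collection day (the first void has no clock window, and is taken as provided), and let q = 1 − p. Under the combined rules, the expected number of subjects with a complete Day 1 who are dropped for a Day 4 miss is N × q³ × (1 − q³). Each has four valid Day 1 samples. With N = 20 there are 20 × 4 = 80 Day 1 samples in all.

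- p = 1%: 20 × 0.9703 × 0.0297 = 0.58 subjects; 4 × 0.58 ≈ 2.3 of 80 samples.
- p = 2%: 20 × 0.9412 × 0.0588 = 1.11 subjects; about 4.4 of 80.
- p = 5%: 20 × 0.8574 × 0.1426 = 2.45 subjects; about 9.8 of 80.

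These figures assume independent misses. If misses cluster within subjects (assumed intraclass correlation 0.2, beta-binomial), the subject counts fall to 0.29, 0.57 and 1.30. That is 4 × 0.29 ≈ 1.2, 4 × 0.57 ≈ 2.3 and 4 × 1.30 = 5.2 of 80 samples.

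**The case against.** The strongest reply is that there is no real conflict. Section B does not say that only Days 1 and 2 count, and it contains no rule that keeps a Day 4 non-complier. Section D's sentence is worded as an addition, and exclusion rules normally accumulate, so applying both gives a clear answer. Only two days have timed voids, so reading Section B as the first and second collection days is the only way to make its whole sentence applicable. This stands. A reader might infer that Section B retains a subject whom Section D excludes, and that the analysis set depends on which section is followed. The documents do not support that inference, because it treats silence in Section B as inclusion. What remains is a wrong label: the protocol defines Day 2 explicitly, and a reader of Section B alone would not find Day 4.

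A second reply is that excluding incomplete subjects is a stated choice and suits a repeated measures ANOVA, which in its standard form needs complete profiles. That is fair, and the choice is not an error in itself. It does discard valid Day 1 data for a reason unrelated to Hypothesis 1, and an analysis that avoids this is readily available.

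A third reply is that misses should be rare. Volunteers are office staff, residents, students and faculty (Section C), and Section B says "The 2nd, 3rd and 4th void samples will be collected in the office during the designated times". This also stands, and it is why the effect is likely small.

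**Conclusion.** The day label in Section B is wrong as worded and should be corrected. It is probably a slip, and Section D's general rule already covers Day 4. The conclusion about the wording rests on the text alone and needs no assumption.

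The cost of dropping whole subjects is real in kind but unknown in size. The illustrative range of about 1 to 10 of 80 Day 1 samples rests entirely on assumed miss rates and an assumed pattern of clustering. A reader might also infer that the study is underpowered as a result. That is not shown: the 87% does not depend on the rule's wording, no miss rate is given, and recruitment may exceed 20. The point is minor.

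**What to change.** 1. Reconcile the exclusion days in Section B with Table 1 (Day 1 and Day 4), have the investigators confirm that this was the intent, and use the same sentence in Section D.
2. Set only the missed or off-window sample to missing and keep the subject's other valid samples.
3. Analyse with a mixed model: fixed effects for condition (Day 1 or Day 4), time slot and their interaction, and random effects for subject and for subject-by-day, with small-sample degrees of freedom. The subject-by-day term ensures that the condition effect is judged against day-to-day variation within subjects.
4. Keep the planned repeated measures ANOVA in fully compliant subjects as a sensitivity analysis, and report missing samples by day and slot.

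The cost is a few words in two sections and slightly more analysis work. Void times are already recorded, so no new data are needed. The downside is reliance on a missing-at-random assumption: given the observed data, whether a sample is missing must not depend on its unseen value. The fully compliant analysis helps to examine that assumption but cannot prove it.
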